## Introduction

Colorectal cancer is the third most commonly diagnosed cancer in the world. It accounts for 11% of all cancer diagnoses, and is the fourth leading cause of cancer mortality, with 1.8 million new cases and approximately 861,000 deaths in 2018 (GLOBOCAN CHI database). Surgical resection is the mainstay of therapy for patients with non-metastatic disease, and has a significant impact on the long-term survival of patients with metastatic disease (3). Outcome is closely related to the quality of preoperative staging, surgery, and multidisciplinary patient management (4-5).

Anastomotic dehiscence (AD) is the most feared complication following resective colorectal surgery due to the high rate of morbidity and mortality that results from the worsening of the overall and oncological outcome of the patient and the increase in the time and costs of hospitalization (6). The International Study Group of Rectal Cancer has defined AD as “a communication between intra and extra luminal compartments due to a defect in the integrity of the intestinal wall at the anastomosis between intestinal segments” (7). In literature the mortality rate resulting from AD is very variable.

An Australian study of 1,598 patients recorded a mortality rate of 1.7% (8), but other case studies report a higher percentage, up to 29%. (9-10-11). Approximately 1/3 of deaths following colorectal surgery are attributable to this complication (12).

The incidence varies depending on the anatomical location of the anastomosis: 1--20% in the case of colorectal anastomosis; 0--2% in the case of colo--colic anastomosis and 0.02--4% in the case of ileo--colic anastomosis (13--14--15--16). Risk factors for anastomotic leakage can be divided into preoperative, intraoperative, and postoperative factors.

All can be traced back to two main groups: local, related to the surgical technique, and general, related to the patient. As regards local factors, the most significant are: experience of the surgeon (especially in the case of laparoscopic surgery), distance from the anal margin, suturing of the anastomosis using manual or mechanical staples, type of anastomosis (lateral--to--side, end--to--side, end--to--end), tension, vascularization and hemostasis of the anastomotic ends, presence of a

protective stoma, placement of drains, bowel preparation, role of the microbiome (17). Review from 2015 identified several patient-related modifiable and non-modifiable risk factors, including: male sex, smoking, habits, alcohol consumption, obesity, diabetes, vascular disease, use of anti-inflammatory drugs, transfusions, hypoalbuminemia, anemia, intraoperative hypotension and use of cardio-vascular drugs, neoadjuvant radiotherapy and chemotherapy(18).

A factor that occurs in almost all these conditions is an alteration in tissue perfusion, and therefore in oxygen availability with consequent micro-ischemia of affected segments and failure of the anastomosis.

Reduced availability of oxygen, in addition to the patient's condition, which can affect it both pre- and post-operatively, can also occur intraoperatively. Good tissue oxygenation can favorably influence the outcome of anastomoses. One study in fact has documented a reduction in the risk of AD following colorectal and gastric surgery with the administration of supplemental oxygen alone (FiO2 80%) during the procedure and for 6 hours thereafter (19).

However, the availability of O2 is not determined exclusively by the inspiratory fraction of O2, but by factors present in the equation that defines the Oxygen Availability (DO2):

$$DO_2 = CO \times CaO_2, \text{ where } CaO_2 = (Hb \times SaO_2 \times 1,39) + (0,0031 \times PaO_2)$$

CO: Cardiac Output; CaO2: Arterial Oxygen content

In this equation the portion of DO2 attributable to the dissolved form of O2 in arterial blood (PaO2) is negligible. Therefore the following equation can be considered:

$$DO_2 = CO \times Hb \times SaO_2 \times 1,39$$

Considering all the parameters involved allows to have a more correct and complete idea of peripheral tissue perfusion. There is only one study in literature in which the indexed DO2 (DO2I) is put in relation to the incidence of AD (20). In this study the CO of 75 patients undergoing colonic

resection was monitored via Doppler probe in the esophagus. The results show that patients with a DO2I <400 ml/min/m^2 have a significantly higher risk of developing AD.

The use of the esophageal Doppler probe for monitoring cardiac dynamics is, however, highly invasive and cannot ignore the operator's experience. Furthermore, it requires frequent checks of the correct positioning of the probe itself. It also presents some, albeit rare, contraindications. Currently, there are several methods for cardiovascular monitoring that allow obtaining sufficiently reliable hemodynamic data while being less or absent invasive and easy to interpret. Through non-invasive analysis of the shape of peripheral blood waveform (pulse--contouring volume--clamp technique) by inflating a cuff placed on the patient's finger, it is possible to obtain complete information about volume status and preload, cardiac function and afterload, in an easily usable format (21--22).

To calculate DO2I it is also necessary to know the patient's total hemoglobin (Hb) value, data obtainable with a blood test, normally performed preoperatively. However, during the surgical intervention, numerous factors contribute to modifying the Hb concentration, such as the patient's volume status and blood loss.

To obtain reliable intraoperative data, it would therefore be necessary to resort to serial blood sampling, venous or arterial which is clearly invasive for the patient and an expenditure of economic resources. Currently, there are new-generation pulse oximeters on the market that analyze different wavelengths and simultaneously measure multiple parameters: O2 saturation, heart rate, respiratory rate, total hemoglobin, carboxyhemoglobin, and methemoglobin, arterial O2 content, perfusion index, and plethysmographic variability index.

With this new technology it is therefore possible to obtain non-invasively and continuously more real and complete data, little influenced by patient movement and by conditions of low perfusion (23--24).

Aim of the study

To evaluate the effects of DO2I on the incidence of AD in patients undergoing laparoscopic resection for colorectal cancer.

## Materials and Methods

Patients attending the General Surgery Unit of the S. Eugenio Hospital in Rome will be enrolled who meet the following inclusion criteria:

- age > 18 years

- candidates for laparoscopic colorectal surgery in elective for neoplastic pathology

Patients will be excluded if they meet the following criteria:

- age < 18 years

- inability to express valid informed consent

- interventions that involve other areas of the body in addition to the colon and rectum

- emergency interventions

- open surgical interventions

- patients who have contraindications to the use of the volume--clamp system for hemodynamic monitoring (conditions that alter significantly the perfusion of the fingers, e.g. Raynaud's disease)

Each patient will follow a preoperative evaluation according to the clinical standards of the Anesthesia and Intensive Care Unit of the two recruiting centers: a complete physical examination will be conducted for all areas and a medical history aimed at identifying general and specific risk factors, and assigning a risk class of the American Society of Anesthesiologists (ASA).

During the preoperative period a blood sample will be taken for a complete blood count coagulation tests, and chemistry tests.

All patients will be given a dedicated informed consent form which will explain the aims and methods of the study. Furthermore, all patients will be informed that the anesthesiological care is of equal intensity in each case, in accordance with the dictates of common and good clinical practice.

Patients will be subjected to general anesthesia (GA) with titrated doses of propofol 1%, fentanyl, rocuronium, desflurane, oxygen, and air, with complete noninvasive monitoring.

All enrolled patients will also be provided with non-invasive hemodynamic monitoring for the calculation of CO based on pulse-contouring type volume clamp, via the ClearSight system (Edwards Lifescience Corporation--USA). Non-invasive monitoring will also be applied for oxygen calculation using pulse oximetry sensors Masimo rainbow (Masimo Corporation – Irvine, California). The DO2I will be calculated at three moments and periods during the procedure: 5 minutes after the induction of GA, 30 minutes after the induction of pneumoperitoneum, 5 minutes after the end of pneumoperitoneum. This is intended to record the variation in DO2I in relation to the hemodynamic changes induced by pneumoperitoneum.

All patients enrolled will constitute Group A. Based on the average of three measurements of DO2I obtained during the intervention, patients in Group A will be distributed into three subgroups: DO2I <400 ml/min/m^2 (Group A1), DO2I 400--600 ml/min/m^2 (Group A2), DO2I >600 ml/min/m^2 (Group A3). The values of DO2I chosen as cut-offs for the formation of the three subgroups were established by analyzing the studies by Levy and by Shoemaker (20--25). For each of the three subgroups the incidence of AD will be calculated, also in relation to anamnestic risk factors.

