## **Statistical Analysis**

The data will be analyzed using the IBM SPSS software package (Armonk, NY), with calculation of medians and standard errors. For continuous variables, the t-test and ANOVA will be used. For categorical variables, the Fisher's exact test will be used. A p value < 0.05 will be considered statistically significant.

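### The plan enrols at one hospital but refers to two recruiting centres; if two do recruit, the pooled anastomotic dehiscence comparison could carry a centre difference into the DO2I result

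*Combined protocol and SAP*

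**What the plan says.** Materials and Methods opens the eligibility text with a single source of patients: "Patients attending the General Surgery Unit of the S. Eugenio Hospital in Rome will be enrolled". A few lines later the preoperative evaluation is to follow the clinical standards of the "Anesthesia and Intensive Care Unit of the two recruiting centers". The second phrase says that two centres recruit, not merely that a second unit helps with assessment.

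The same section then pools the patients: "All patients enrolled will constitute Group A". They are divided only by mean intraoperative DO2I, into A1 (below 400 ml/min/m²), A2 (400 to 600) and A3 (above 600). For each subgroup "the incidence of AD will be calculated, also in relation to anamnestic risk factors". Anamnestic factors come from the patient's history; centre is not one of them, and no model is named.

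Statistical Analysis gives the test that applies to AD: "For categorical variables, the Fisher's exact test will be used". The threshold is given as "A p value < 0.05 will be considered statistically significant". The t-test and ANOVA are for continuous variables and do not bear on the AD comparison. No stratification or centre term appears anywhere.

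**The concern.** The number of recruiting centres defines the study population, and a reader cannot tell from the text whether it is one or two.

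It also bears on the analysis. DO2I is observed, not randomised, so nothing in the design balances centre across A1, A2 and A3. The Introduction names surgeon experience, suturing method and type of anastomosis among the main local risk factors for AD, and these could differ between surgical teams. Its DO2 equation contains cardiac output and haemoglobin, and the text says that volume status and blood loss alter haemoglobin during surgery. Local practice could therefore shift DO2I. If both happened, a test that ignores centre would attribute some of the centre difference to DO2I, which is the effect the study sets out to evaluate.

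**Working it through.** **Figure to reproduce.** There is none. The documents state no sample size, expected event count, effect size or centre-level rate. What follows is an illustration, and its inputs are assumptions.

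**Set-up.** Two centres, A and B, of equal size. AD risks are p_A and p_B. The shares of patients in subgroup A1 are l_A and l_B. Within each centre DO2I has no effect on AD. Write L = l_A + l_B.

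- Pooled risk in A1: r1 = (l_A·p_A + l_B·p_B) / L
- Pooled risk in the rest: r0 = [(1 − l_A)·p_A + (1 − l_B)·p_B] / (2 − L)
- Subtracting: r1 − r0 = (l_B − l_A)(p_B − p_A) / [L(2 − L)]

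The last line shows that the bias is a product. It vanishes if the two centres have the same AD risk or the same share in A1. If the centre with more A1 patients has the lower AD risk, the product is negative, and a real harm of low DO2I would be partly hidden.

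**Three assumed scenarios.** The rates lie inside the range quoted in the Introduction, "1--20% in the case of colorectal anastomosis". L = 0.7 in all three.

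| AD risk, A v B | A1 share, A v B | r1 | r0 | Spurious risk ratio |
|---|---|---|---|---|
| 4% v 10% | 20% v 50% | (0.008 + 0.050)/0.7 = 0.0829 | (0.032 + 0.050)/1.3 = 0.0631 | 1.31 |
| 3% v 12% | 20% v 50% | (0.006 + 0.060)/0.7 = 0.0943 | (0.024 + 0.060)/1.3 = 0.0646 | 1.46 |
| 5% v 10% | 25% v 45% | (0.0125 + 0.045)/0.7 = 0.0821 | (0.0375 + 0.055)/1.3 = 0.0712 | 1.15 |

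**False-positive rate of the pooled test.** Simulated two-sided Fisher's exact test, A1 versus the rest, at 0.05, with no true DO2I effect. The plan does not state sidedness; two-sided is assumed. Total sizes of 100, 200 and 400 are also assumed.

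| Scenario | N = 100 | N = 200 | N = 400 |
|---|---|---|---|
| Risk ratio 1.31 | 4.7% | 7.0% | 9.8% |
| Risk ratio 1.46 | 6.8% | 10.8% | 16.6% |
| Risk ratio 1.15 | 3.6% | 4.7% | 5.9% |

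A repeat simulation agreed to within 0.7 percentage points. In the same scenarios a centre-stratified Mantel-Haenszel test with continuity correction rejected no more than about 3.3% of the time.

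**How far it can go.** A more extreme assumption, AD 2% v 15% and A1 shares of 20% v 60%, gives a spurious odds ratio of 1.97. Pooled Fisher rejection is then 13%, 24% and 44% at the three sizes, against about 2.5% for the stratified test at N = 200. That needs large centre differences in both quantities at once. When either quantity is equal across centres, the odds ratio is 1.00 and pooled rejection stays below 5%.

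**The case against.** A reader might infer that the comparison is confounded by centre, or that the planned test is invalid. The documents do not support either. Confounding needs three things: a second recruiting centre, a different AD rate there, and a different DO2I distribution there. The text hints at the first and reports nothing on the other two.

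Some of the text points the other way. Materials and Methods gives one list of anaesthetic drugs, one cardiac-output system, one oximetry sensor and one measurement schedule for all patients, and says that anaesthetic care is equally intensive in every case. The anaesthesia unit is named in the singular, so a shared service is possible. This weakens the link from centre to DO2I but does not remove it: doses are titrated, no fluid or haemodynamic rule is stated, and the singular may be an artefact of translation.

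The inflation in the three main scenarios is also small to moderate, and close to nil in the mildest at the smaller sizes. Centre is not the best-documented confounder either. Anastomotic site and haemoglobin have clearer support in the Introduction, and stratifying by centre would not deal with them.

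Finally, title and contact pages were removed before review and may name a second centre, so the missing name is not a fault. What stands is the conflict between the two sentences, and the absence of centre from the analysis if two centres do recruit.

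**Conclusion.** The contradiction within Materials and Methods is real and unresolved in the available text. The statistical consequence is conditional. If two centres recruit and differ in both AD rate and DO2I, the pooled Fisher comparison would show part of the centre difference as a DO2I effect. The illustrative spurious risk ratios of 1.15 to 1.46 rest on assumed centre rates, assumed A1 shares, equal enrolment and no within-centre effect. The actual size cannot be computed from the documents, and the bias is zero if either quantity is equal across centres. If only one centre recruits, this is a wording error and nothing more. The point merits action because the remedy is cheap and the adjustment is better chosen before results are seen, not because the planned analysis has been shown to fail.

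**What to change.** Reconcile the enrolment sentence and the preoperative-evaluation sentence in Materials and Methods.

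- **If two centres recruit:** name both in the enrolment sentence and record centre for every patient. In Statistical Analysis, make the main AD comparison across A1, A2 and A3 centre-stratified, using an exact stratified test or the generalised Cochran-Mantel-Haenszel test. If the main contrast is A1 versus the rest, the ordinary Mantel-Haenszel test suffices. Report the pooled Fisher result as secondary. No regression model is needed.
- **If one centre recruits:** correct the reference to two recruiting centres. No change to the analysis is needed.

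The cost is one sentence in Methods and, in the two-centre case, one recorded variable and one sentence in Statistical Analysis. The statistical price is about one degree of freedom, felt as a small loss of precision when AD events are few.

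### The reading before pneumoperitoneum is tied to anaesthetic induction rather than insufflation, so changes in DO2I between readings cannot be attributed to pneumoperitoneum alone

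*Combined protocol and SAP*

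**What the plan says.** Materials and Methods has DO2I calculated at three times: "5 minutes after the induction of GA, 30 minutes after the induction of pneumoperitoneum, 5 minutes after the end of pneumoperitoneum". These are called readings 1, 2 and 3 below.

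It gives the purpose as recording the variation in DO2I "in relation to the hemodynamic changes induced by pneumoperitoneum". The same section forms the three DO2I subgroups from the average of the three readings.

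The Introduction reduces oxygen delivery to DO2 = CO × Hb × SaO2 × 1.39. It also notes that during surgery "numerous factors contribute to modifying the Hb concentration, such as the patient's volume status and blood loss", and presents continuous non-invasive oximetry as the way to follow Hb. Under Materials and Methods, every patient has both a CO monitor and the oximetry sensors. Statistical Analysis names the t-test and ANOVA for continuous variables and does not mention within-patient change.

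**The concern.** The schedule has a stated purpose, so it is fair to ask whether the differences between readings serve it.

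**First change (reading 1 to 2).** Reading 1 is timed from anaesthetic induction. The plan does not fix the interval from there to insufflation, and nothing is logged immediately before insufflation. Any further movement of CO as the anaesthetic settles is counted together with the effect of pneumoperitoneum.

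**Second change (reading 2 to 3).** Reading 2 comes 30 minutes into pneumoperitoneum and reading 3 comes 5 minutes after it ends. The rest of the pneumoperitoneum lies between them, and the Introduction itself expects Hb to move during surgery.

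There is no comparison group without pneumoperitoneum, and no contrast between readings is specified. A reported fall or rebound in DO2I could therefore be credited to pneumoperitoneum when part of it, or all of it, has another source.

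**Working it through.** The plan states no figure for this variation, so there is none to reproduce. The check is of timing, followed by illustrations from the plan's own equation. Every effect size below is assumed. Indexing divides by body surface area, which is constant within a patient, so percentage changes are the same for DO2 and DO2I.

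**1. Order and spacing.** Let insufflation occur g minutes after anaesthetic induction and pneumoperitoneum last T minutes. The plan gives neither.

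- Reading 1 is at 5 minutes after induction and reading 2 at g + 30, so the gap is g + 25 minutes.
- After insufflation, reading 2 is at 30 minutes and reading 3 at T + 5, so the gap is T − 25 minutes. For T = 120 to 240 (assumed), that is 95 to 215 minutes.

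The readings therefore do lie before, during and after pneumoperitoneum.

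**2. Induction effect on the first change.** Suppose pneumoperitoneum truly lowers CO by 10%, with Hb and SaO2 constant, and reading 1 differs from the value just before insufflation by s. The apparent change is 0.90/(1 + s) − 1.

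| s (assumed) | Calculation | Apparent change |
|---|---|---|
| −15% | 0.90/0.85 − 1 | +5.9% |
| −10% | 0.90/0.90 − 1 | 0% |
| +10% | 0.90/1.10 − 1 | −18.2% |

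**3. Hb drift in the second change.** DO2I is proportional to Hb. A fall from 12 to 11 g/dL gives 11/12 = 0.917, a loss of 8.3%. A true 8% rebound in CO on release would then read as 1.08 × 0.917 = 0.99, or −1%. Hb falls of 0.5 and 1.5 g/dL from 12 give losses of 4.2% and 12.5%.

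**4. What can be recovered from the three readings.**

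- *Separate components.* In step 3, CO alone shows +8% and Hb alone −8.3%, so examining them separately removes the Hb problem. It does not help in step 2, where the shift is in CO itself.
- *Reading 2 against the mean of readings 1 and 3.* If Hb is 5% down at reading 2 and 10% down at reading 3, the true −10% is recovered: (0.90 × 0.95)/((1 + 0.90)/2) = 0.855/0.95 = 0.90. This needs equal drift in the two intervals.
- *The same contrast with unequal intervals.* Take g = 30 and T = 180, so the gaps are 55 and 155 minutes, with Hb falling linearly from 12 to 11. Hb at reading 2 is 12 − 55/210 = 11.74, a ratio of 0.978. The result is (0.90 × 0.978)/((1 + 0.917)/2) = 0.880/0.958 = 0.919, or about −8%.
- *The same contrast with reading 1 15% low and no drift.* The result is 0.90/((0.85 + 1)/2) = 0.90/0.925 = 0.973, or −2.7% in place of −10%.

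The induction effect is thus the part that neither separating the components nor averaging readings 1 and 3 removes.

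**5. What a pre-insufflation reading would do.** With the same linear Hb drift, Hb just before insufflation is 12 − 25/210 = 11.88. The change to reading 2 is 0.90 × 11.74/11.88 = 0.889, or −11.1% in DO2I and −10% in CO. Reading 1 no longer enters the contrast. The 30-minute span still admits some drift.

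**The case against.** The case against making this point is substantial, and most of it stands.

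- A reader might infer that the readings fail to bracket pneumoperitoneum. The schedule has one before, one during and one after it, so that is wrong. The brackets are only loose.
- A reader might infer that the schedule cannot serve its purpose. The plan undertakes only to record variation "in relation to the hemodynamic changes induced by pneumoperitoneum". It promises no isolated causal estimate, and readings before, during and after do record something relevant.
- A reader might infer that no later analysis could help. CO and Hb are separate inputs to each DO2I value, and the plan chose continuous oximetry because Hb shifts. Examined separately, they dispose of the Hb example, and steady drift can be partly averaged out.
- No specified result depends on these differences. The aim concerns DO2I and AD, the grouping uses the average, and Statistical Analysis specifies no change between readings.
- All the magnitudes are assumed, and some were chosen to match the effect they hide. They show what is possible, not what is likely.
- The added pre-insufflation contrast still spans 30 minutes of surgery.

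What remains is the anchoring of reading 1. Its interval to insufflation is open, and a shift in CO after induction survives both repairs. The plan also does not say that CO and Hb will be reported separately, so the protection against Hb drift is available but not secured.

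**Conclusion.** The point holds as a minor limitation. Differences between the three readings cannot be attributed to pneumoperitoneum alone. Evolving induction effects on CO can enter the first change, and blood loss or dilution can enter the second through Hb unless CO and Hb are looked at separately.

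The documents give no basis for the size. Under the assumed values, the distortion can be as large as the effect itself: a true 10% fall could appear as anything from an 18.2% fall to a 5.9% rise.

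The consequence is confined to the secondary descriptive purpose stated in Materials and Methods. A reader might extend it to the subgroups or to the AD comparison, but both rest on the average level of DO2I, not on its change between readings, so the documents do not support that extension.

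**What to change.** In Materials and Methods, add two logging times from the monitors already running: immediately before insufflation and immediately before release. At these and at the present three times, record CO, Hb, SaO2 and DO2I.

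Define the pneumoperitoneum variation as two within-patient changes:

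- 30 minutes after insufflation minus just before it
- 5 minutes after release minus just before it

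Report CO and Hb separately alongside DO2I, and note that the first contrast still covers 30 minutes of surgery. State that the average used to form the subgroups stays on the present three readings, so the grouping rule does not change.

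The cost is two more logged time points per patient and a short addition to the text, with no added procedure or staff. If the extra logging is declined, the alternative is to narrow the purpose statement so that the differences are presented as descriptive and not attributed to pneumoperitoneum.

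### Does grouping patients by the average of three DO2I readings lose the pneumoperitoneum effect the readings are taken to record?

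*Combined protocol and SAP*

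**What the plan says.** Materials and Methods fixes three times for DO2I. The first is five minutes after anaesthesia is induced; the others are "30 minutes after the induction of pneumoperitoneum, 5 minutes after the end of pneumoperitoneum". The stated purpose is to record how DO2I varies "in relation to the hemodynamic changes induced by pneumoperitoneum".

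The same section then forms three subgroups, "Based on the average of three measurements of" DO2I: A1 below 400, A2 from 400 to 600 and A3 above 600 ml/min/m². The outcome comparison is: "For each of the three subgroups the incidence of AD will be calculated, also in relation to anamnestic risk factors".

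The aim, at the end of the Introduction, is "To evaluate the effects of DO2I on the incidence of AD". The Introduction also says that reduced oxygen availability "can also occur intraoperatively", and that in one earlier study of 75 patients those with DO2I below 400 "have a significantly higher risk of developing AD".

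Statistical Analysis is generic: summaries "with calculation of medians and standard errors", t-test and ANOVA for continuous variables, Fisher's exact test for categorical ones. It assigns no method to the separate DO2I readings.

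**The concern.** The schedule seems designed to capture what pneumoperitoneum does to oxygen delivery, yet the grouping rule folds the three readings into one number. The only reading taken during pneumoperitoneum carries one third of the weight. A patient with a marked dip and two good readings joins a patient who was steady throughout.

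If low DO2I during pneumoperitoneum is what drives AD, patients who had it would be spread over A1, A2 and possibly A3. The contrast between A1 and the rest would shrink, and a weak result could reflect either no effect or an exposure summary that missed it. The stated reason for taking three readings would also have no named analysis.

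**Working it through.** The plan states no sample size, power or expected DO2I distribution, so there is no figure of its own to reproduce. The check has four parts.

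**1. The grouping rule (exact, no assumptions).** Let P be the pneumoperitoneum reading and B the mean of the other two. The average is (P + 2B)/3. It is at least 400 when B ≥ (1200 − P)/2.

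| P | B needed for A2 or higher |
|---|---|
| 380 | (1200 − 380)/2 = 410 |
| 350 | (1200 − 350)/2 = 425 |
| 300 | (1200 − 300)/2 = 450 |

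Examples:
- 450/310/450: 1210/3 = 403.3, so A2.
- 600/300/600: 1500/3 = 500, the middle of A2.
- 700/390/720: 1810/3 = 603.3, so A3.
- 390/420/380: 1190/3 = 396.7, so A1, although the pneumoperitoneum reading is above 400.

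The two summaries can thus disagree in either direction.

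**2. Do the documents favour the single reading?** The aim names DO2I without a phase of surgery. All three readings are intraoperative, so the Introduction's remark about intraoperative loss of oxygen supply applies to their average as much as to any one of them. The Introduction does not say whether the 400 threshold came from a mean, a minimum or a single value. The purpose given for the schedule is to record variation, and three stored readings do that. Nothing says the variation must be related to AD.

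**3. How large could it be? (assumptions only)** The documents give no DO2I mean, standard deviation, correlation or fall, and do not say that DO2I falls at all. The following was assumed: normal readings, mean 450 to 550 outside pneumoperitoneum, standard deviation 20 to 25% of that mean, equal correlations 0.5 to 0.8.

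| Assumed mean fall | Share of patients with P < 400 who are not in A1 | Same, as share of all patients |
|---|---|---|
| none | 18 to 62% | 3 to 11% |
| 10% | 27 to 69% | 10 to 20% |
| 20% | 34 to 73% | 20 to 30% |

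Hand check at mean 500, fall 10%, standard deviation 100, correlation 0.7: P has mean 450, so Pr(P < 400) = Φ(−50/100) = 0.309. The average has mean (500 + 450 + 500)/3 = 483.3 and standard deviation 100 × √((1 + 2 × 0.7)/3) = 89.4, so Pr(A1) = Φ(−83.3/89.4) = 0.176. The simulation gave 0.308 and 0.176.

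The width of these ranges shows that they mostly reflect the inputs.

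**4. Is the dilution one-sided?** Assume an AD risk of 12% below 400 and 4% otherwise, a true ratio of 3.0.

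| Assumed mean fall | AD follows P, grouped by average | AD follows average, grouped by P |
|---|---|---|
| 10% | 1.77 to 2.37 | 1.59 to 2.30 |
| 20% | 1.49 to 1.99 | 1.52 to 2.25 |

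The loss is of similar size either way. These figures also treat every within-patient difference as real. If part of it is independent device error, say with standard deviation 40 per reading, the average carries 40/√3 = 23.1, which favours the average.

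**The case for a change.** The best case for a change is that the mismatch is real and cheap to close. The protocol gives a reason for the timing of the readings, and no section names an analysis that serves it. ANOVA of DO2I over time, even if read into Statistical Analysis, would not link the pneumoperitoneum reading to AD. A comparison chosen after the results are known would be post hoc, while a few sentences now would prespecify it with no new measurements.

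Part of this stands. The separate readings have no named analysis, and any later comparison of AD by a single reading would have to be labelled post hoc.

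The claimed benefit does not stand. The Introduction puts AD at 0 to 2% for colo-colic, 0.02 to 4% for ileo-colic and 1 to 20% for colorectal anastomoses. At 4%, 100 patients would yield 4 events across three subgroups. A second Fisher's exact test on so few events would rarely show whether a weak result means no effect or the wrong summary. Statisticians would also differ on which second summary to use: the pneumoperitoneum value, the lowest value or the change from the first reading. The documents do not settle that choice.

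**Conclusion.** No change follows. Averaging leaves the variation out of the grouping, not out of the data. Comparing AD across A1, A2 and A3 is a valid analysis of average intraoperative DO2I and answers the stated aim. Describing DO2I at each time point is routine reporting of a recorded continuous variable, and the general wording of Statistical Analysis leaves room for it.

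The certain part is small: a patient below 400 during pneumoperitoneum is classed A2 or higher whenever the other two readings average at least (1200 − P)/2. How often this would happen is unknown, and every percentage and risk ratio above depends on inputs the documents do not supply. Under those inputs, replacing the average by the single reading offers no clear gain.

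This conclusion rests on the documents being silent about which phase of surgery matters for AD. If the sponsor held evidence that the pneumoperitoneum phase is decisive, the choice of summary would deserve another look.
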